# 3. Subjects

### 3.1 Study populations

This study will recruit a maximum of 80 adults (aged between 18 and 79 years old) with non-penetrating TBI and a comparison group of up to 20 healthy volunteers matched to the TBI cohort for sex and age within 5 years. The healthy volunteers will only undergo brain imaging assessments, blood collection and a subset of questionnaires and neuropsychological testing. The healthy volunteers will not participate in the intervention phase. Withdrawals or dropouts will be replaced to have at least 20 subjects with TBI in each group to complete the second assessment visit. An eligibility checklist is included in Appendix 3A and B.

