#### B. Rapid-resistive exercise training (RET)

Subjects will perform physical exercise on an elliptical trainer, with emphasis on maintaining a near maximal speed of movement for 30 minutes. The session will also include 15 minutes of warm-up and cool-down at a slower speed. Subjects will be encouraged to progressively increase their maximal speed over time, while maintaining a smooth rhythm throughout the session. Once the subject has reached a speed of 80 RPM, resistance will be added. It will be increased incrementally as long as adding resistance does not decrease their speed below 80 RPM and does not increase their heart rate beyond the target set for moderate exercise as described below. Rapid-resistive exercise will be continuous over the 30 minutes unless the patient cannot tolerate the regimen continuously. If the training regimen cannot be tolerated, exercise at near maximal speed of movement is achieved. The primary goal of this type of exercise is to increase movement speed and reciprocal coordination, while being within moderate intensity. Subjects in

RET would be exercising below their anaerobic threshold (determined from the CPET), which is typically about 50% HRR and maximal  $VO_2$ . Therefore, the heart rate associated with ~85% of each subjects' anaerobic threshold would be determined and this target heart rate would not be exceeded during their exercise sessions to ensure exercise is of moderate intensity. A paper-based log sheet will be used to record the heart rate, resistance and speed used in each session (Appendix 9).

Subjects in the exercise training group will complete at least 30 of the 36 training sessions in twelve weeks to remain eligible for the study. Subjects will wear a heart rate monitor during the sessions such that beat by beat heart rate is displayed continuously. The frequency of the sessions will be three times per week, unless make up sessions are needed to adhere to the minimum sessions required. Sessions will be supervised by credentialed RMD personnel.

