Subjects randomized to the wait-list control will be further randomized to either AET or RET after Assessment Visit 2. In the first 3 months, subjects in the wait-list control will receive no exercise training; however they will be contacted monthly to ensure compliance and to maintain contact (Appendix 10). For subjects initially randomized to either AET or RET, they will no longer follow a formal exercise intervention at NIH following Assessment Visit 2. However, they will be contacted monthly for the next 3 months and asked about their weekly physical activities (Appendix 10).

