# 8. Outcome measures

### 8.1 Primary Outcome

The primary outcome measure for this study is the change in cognitive function as measured by Trail Making Test Part B (TMT-B). This is measured as the difference in the time taken to complete the test between pre and post-exercise intervention and compared to the control group. Standardized t-scores will be used to interpret the results of this test.

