# 9. Statistical Analysis

### 9.1 Analysis of data

The primary analysis is a mixed model (with time as the within-subject factor and exercise group as the between subject factor) analysis of variance (ANOVA) which will be used to determine significant differences in the primary (ANOVA) and secondary outcome variables (MANOVA by outcome category – i.e. motor, cognitive, behavioral, etc – to help control for multiple comparisons) as a result of exercise. Therefore, the data will include the time points immediately pre and post exercise for all subjects. We are interested in both main effects for time and exercise as well as potential interaction effects between exercise group and time.

All subjects completing the protocol and not withdrawing or presenting off study criteria will be included in the analyses. Secondary analyses related to protocol adherence and other aspects of feasibility are anticipated. Estimation of the necessary and sufficient sample size was calculated for a large effect change in the main outcome variable, pre- to post-training change in executive functioning. Significance will be set at p < 0.05.

While we do not anticipate that subjects will improve over time in the absence of exercise, we have included a waitlist control to evaluate this, and we will compare the amount of change over time in the control group versus the exercise group that were not waitlisted using an independent t-test. Also for the exercise group that was not waitlisted, there will be a three month follow up period evaluated to determine whether there is any change compared to the end of the exercise period using paired t-tests.

The change in aerobic capacity and fast elliptical speed will be correlated with changes in the other outcomes measures. Baseline dopamine transmission scores will also be correlated with all motor outcomes using linear regression.

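### Section 9.1 analyses completers only, after removals that follow randomisation and with losses replaced, so the month-3 exercise versus wait-list comparison is not made as randomised; the direction and size of any bias cannot be determined

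*Combined protocol and SAP*

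**What the plan says.** The analysis set is given in one sentence of section 9.1: "All subjects completing the protocol and not withdrawing or presenting off study criteria will be included in the analyses". Section 4.1 places randomisation after the baseline assessments, so every later removal follows it. The removal rules are:

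- **Attendance (4.4.7):** exercise subjects "will complete at least 30 of the 36 training sessions in twelve weeks to remain eligible for the study". Sessions are three a week "unless make up sessions are needed to adhere to the minimum sessions required".
- **Withdrawal criteria (7.3):** clinically significant worsening of mood or behaviour, changes in care that could affect the outcomes, non-compliance, and an assessment that cannot be rescheduled within four weeks.
- **Pregnancy (10.3.2).**

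Losses are made up. Section 3.1 says: "Withdrawals or dropouts will be replaced to have at least 20 subjects with TBI in each group to complete the second assessment visit". Section 7.3 also provides for replacement.

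Two analyses bear on the primary outcome, Trail Making Test Part B (TMT-B). Section 9.1 calls a mixed ANOVA primary, for which "the data will include the time points immediately pre and post exercise for all subjects". It also plans to "compare the amount of change over time in the control group versus the exercise group that were not waitlisted using an independent t-test". Section 8.1 defines the outcome as "the difference in the time taken to complete the test between pre and post-exercise intervention and compared to the control group". On the wait-list arm, 4.4.7 says: "In the first 3 months, subjects in the wait-list control will receive no exercise training".

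There is no all-randomised analysis set, no method for missing outcomes, and no plan to collect outcomes from removed subjects. Section 16.2 treats missed assessments only as a reporting matter.

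**The concern.** The month-3 contrast with the wait-list is the only comparison with an unexercised control. Randomisation protects it only if subjects are analysed in the arms to which they were assigned. Here the set is chosen by events after assignment, and one of those events, missing more than six of 36 sessions, cannot occur in the control arm during the period compared. If poor attenders would also have improved less (or more) on TMT-B, the exercise mean shifts with no treatment effect at all.

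Replacement restores the counts but not the comparison, and the final numbers need not reveal unequal losses. Completing the protocol is also undefined: it could mean 30 sessions (4.4.7), the second assessment visit (3.1 and 9.2) or the final visit (4.1). On the last reading, a subject lost after month 3 would also drop out of the month-3 comparison.

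**Working it through.** **1. How many randomised subjects could be left out.** Section 9.2 wants 60 completers, states attrition of about one-third, and recruits 80. The 80 is reproduced by 60 × (1 + 1/3) = 80. Losses implied by these figures are 80 − 60 = 20, or one-third of 80 = 26.7. Since 80 is a recruitment maximum and some attrition may precede randomisation, post-randomisation loss could be anything from 0 to about 27. Neither its split by arm nor its cause is given.

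**2. Which analysis is affected, and how.** In the month-3 comparison the session rule acts on the exercise arms only; the other rules act on all arms. In the pre/post-exercise ANOVA, wait-list subjects enter through their own later training, so the session rule is not one-sided. That set is still selected after randomisation.

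**3. Illustration of size.** Assumptions, none from the documents: no true effect; TMT-B change has SD 1; attendance and improvement are jointly normal with correlation ρ = 0.3 or 0.5; the lowest-attending fraction q of the 54 exercisers is removed; all 26 controls remain.

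Shift in the exercise mean = ρ × φ(z_q) / (1 − q), where φ is the normal density at the q-quantile. For q = 1/3, φ = 0.3636, so the shift is 0.3 × 0.3636 / 0.6667 = 0.164. Dividing by √(1/36 + 1/26) = 0.257 gives a non-centrality of 0.636, and the two-sided 5% t-test then rejects 9.6% of the time.

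| Removed | n | Shift, ρ = 0.3 / 0.5 | Type I error |
|---|---|---|---|
| 5% | 51 v 26 | 0.033 / 0.054 SD | 5.2% / 5.6% |
| 10% | 49 v 26 | 0.058 / 0.097 SD | 5.7% / 6.8% |
| One-third | 36 v 26 | 0.164 / 0.273 SD | 9.6% / 18.1% |

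A negative ρ reverses the sign. If 10% of controls are lost in the same selective way while one-third of exercisers are (36 v 23), the net shift is 0.105 / 0.175 SD and type I error is 6.7% / 9.9%. With equal, similarly selective loss in both arms, or loss unrelated to outcome, the shift is zero.

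**4. What the pilots say about removal for low attendance.** The threshold is 30/36 = 83.3%. Section 1.2.1, Table 2 gives adherence of 93% (SD 4) in the treadmill aerobic pilot of 10 subjects. A normal tail gives (83.3 − 93)/4 = −2.42, or about 0.8% below the threshold. In Table 3, the rapid-resistive pilot, 5 of the 11 patients with device data were below 83.3% (77.5, 55, 65, 80 and 17.5%), on a different schedule of five days a week for eight weeks. The two point in opposite directions.

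**The case against.** The strongest reply is that no harm is shown. The larger error rates need all the stated attrition to be low attendance, no control loss, and an assumed correlation; no figure in the documents supports any of these. Make-up sessions and supervision should keep removals down. Section 9.1 calls the pre/post-exercise ANOVA primary, and presents the t-test as a check on change without exercise. The Precis hypothesis concerns those who performed the exercise, which a completer analysis partly serves, and 9.1 anticipates secondary adherence analyses. The second assessment visit is the most natural meaning of completion.

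Much of this stands. A reader might infer that the trial's false-positive rate is 10-18%, or that the plan favours exercise. The documents do not support either: the top of that range is a constructed worst case, and the sign is unknown. A reader might also infer that the ANOVA called primary is distorted one-sidedly by the session rule; it is not.

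The opposite inference, that the aerobic pilot shows removal to be negligible, also fails. It covers 10 treadmill subjects, possibly completers, says nothing about rapid-resistive training, and bears on one removal rule only.

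What does not stand is the defence of the analysis set. Section 8.1 defines the primary outcome by comparison with the control group, and neither the hypothesis wording nor the adherence analyses supply an analysis that preserves randomisation.

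**Conclusion.** The point holds on the text, with high confidence. The analysis set is selected after randomisation, one removal rule is one-sided in the month-3 comparison, losses are replaced, and nothing in the plan restores an as-randomised analysis. The amount of removal, and the direction and size of any bias, cannot be established from the documents. The figures above are illustrations that depend on the assumed correlation and loss pattern. This should be fixed on the principle of analysing as randomised. It also needs settling before data collection ends, because month-3 outcomes never collected from removed subjects cannot be recovered later.

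**What to change.** **In 9.1:** compare exercise with wait-list on TMT-B at month 3, before wait-list cross-over, in all randomised subjects in the arm assigned and regardless of sessions attended. Use all available data except data a subject withdraws. Fit a likelihood-based mixed model, and add a delta-adjusted sensitivity analysis by arm for missing month-3 values over a stated range. Report the pre/post-exercise ANOVA separately, labelled as not a randomised comparison with an unexercised control. Keep the completer analysis as a labelled supportive analysis for the Precis hypothesis.

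**In 4.4.7:** still invite subjects with fewer than 30 sessions to the month-3 assessment, unless consent is withdrawn or the protocol's own withdrawal, safety or pregnancy rules preclude it. This is the main gain, since a model with only baseline and month 3 recovers little for a subject with no month-3 value.

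**Reporting and consistency:** give numbers randomised, removed (with reason) and analysed, by arm. The sponsor should reconcile 3.1, 4.4.7, 7.3 and 9.1 on who stays in the study and what completing the protocol means. The clinical withdrawal rules are left as they are.

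**Cost:** wording changes and a visit already scheduled for all patients, plus some power lost to dilution. Section 9.1 gives only a large effect; taking d = 0.8 as an assumption, and letting a share s of exercisers be non-adherent and gain nothing, the effect is 0.8 × (1 − s):

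| Observed | s = 5% | s = 10% | s = 1/3 | Completers of the same size |
|---|---|---|---|---|
| Both exercise arms, 36 v 17 | 72% | 67% | 43% | 76% |
| Aerobic arm alone, 18 v 17 | 59% | 54% | 33% | 63% |

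The sizes are two-thirds of 54, 26 and 27. If all 80 are randomised and observed (54 v 26), power is 88%, 85% or 60%, so following up low attenders offsets part of the cost.

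Dropout bias is reduced, not removed. If one-third of exercisers have no month-3 value and truly do 0.2 to 0.5 SD worse than modelled, the estimate moves by 1/3 × 0.2 = 0.07 to 1/3 × 0.5 = 0.17 SD. If 10% are missing, it moves by 0.02 to 0.05 SD.

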#### Rapid-Resistive Exercise Training (RET)

CNS IRB Protocol Template (2.5.15)

Rapid, reciprocal exercise will be performed using an elliptical trainer, which allows for safe fast speed training. Similar to the previous study (10-CC-0150), this type of training will involve rapid movement and coordination of all four extremities. Emphasis will be placed on increasing speed, however resistance can be increased to keep the level of exercise at a light to moderate intensity. Exercise intensity would not exceed ~ 50% of maximal VO2 (moderate intensity).

The objectives of this study are:

- Primary To evaluate the effects of exercise training intensity on cognitive function in patients with TBI
- Secondary To evaluate the effects of exercise training intensity on balance, physical fitness and quality of life in patients with TBI
- Secondary To evaluate the effects of exercise training intensity on structural and functional changes in the brain of patients with TBI
- Secondary To examine the relationship between cognitive, behavioral, and motor outcomes and brain imaging, biomarker and genetic outcomes or variables
- Secondary To examine structural/functional brain differences, blood biomarkers and a subset of cognitive and self-reported outcomes between patients with TBI and healthy volunteers within the same age range

Since the direct effects of physical exercise are well known, the primary focus here is on the effects of exercise on cognitive function and on brain connectivity. While we anticipate that exercise regardless of intensity will improve cognitive and behavioral outcomes, we anticipate that the effects will be greater for the aerobic training group such that when the results are analyzed separately for each exercise condition, only the aerobic group will demonstrate a significant change in the primary outcome measure. Study outcomes such as brain imaging, blood biomarkers, cognitive performance and selfreported questionnaires in patients with TBI will also be compared to a healthy volunteer sample matched to the TBI cohort for sex and age within 5 years.

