### 8.2 Secondary Outcomes

Secondary outcome measures included here are those which have been shown previously or that we hypothesize to improve as results of exercise. Analysis will include comparisons of both exercise groups both combined and separately to the control group, and pre- to post-intervention changes within and across exercise groups in the following:

• Changes in other measures of cognitive function as measured by the

neuropsychological assessments

- Changes in motor assessments including balance and reaction time to perturbations
- Changes in cardiorespiratory fitness as measured by peak VO2 achieved and time on the treadmill
- Change in fatigue severity as measured in the FSS; other quality of life, physical activity, and sleep quality scales will be used to enhance interpretation of the FSS findings
- Changes in MRI findings, both structural and functional measures; e.g., increases in hippocampal brain volume, or increases in the degree of functional connectivity or fractional anisotropy between brain regions that sub serve motor, cognitive and behavioral functioning.
- Changes in biomarkers

We are also interested in examining relationships among various outcomes (functional, behavioral, structural, mechanistic, etc.) in persons with TBI. Therefore, secondary analyses may include correlations or comparisons of baseline measures within and across the groups. Comparisons of outcome measures including blood biomarkers, brain imaging, neuropsychological and questionnaire data will also be made to a reference healthy volunteer sample that is matched for sex and age within 5 years.

Table 4.	Summary	of t	the	Relevant	Outcome	Variables	for	the	Secondary	Outcome
Measures										

Test/Construct Measured	Relevant outcome variable
Gait Speed	Free and fast walking velocity
Dual Task Performance	Cognitive and motor cost (difference between DT and ST performance)
LOS/Dynamic Balance	Reaction time, maximal excursion
Elliptical Speed (reciprocal coordination)	Free and fast cadence on the elliptical
SOT/3 sensory systems	Equilibrium score for each sensory system
MCT/involuntary reaction time	Mean latency of responses
Adaptation/stability when perturbed	Sway velocity in 2 conditions

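### The waitlist-versus-exercise t-test on change in section 9.1 does not use baseline TMT-B as a covariate; a common-slope ANCOVA is a cheap efficiency improvement of unknown size, not the repair of an error

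*Combined protocol and SAP*

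**What the plan says.** Section 8.1 makes change in TMT-B the primary outcome and requires comparison with the control group. "This is measured as the difference in the time taken to complete the test" before and after the intervention, and "Standardized t-scores will be used to interpret the results of this test".

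Section 9.1 labels a time-by-group mixed ANOVA as primary, for which "the data will include the time points immediately pre and post exercise for all subjects". Separately, to check that patients do not improve without exercise, it will "compare the amount of change over time in the control group versus the exercise group that were not waitlisted", using an independent t-test. Neither section names a covariate. Section 4.1 places all baseline assessments before randomisation.

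Section 8.2, on secondary outcomes, plans "comparisons of both exercise groups both combined and separately to the control group". Section 2 expects that "when the results are analyzed separately for each exercise condition, only the aerobic group will demonstrate a significant change". Section 9.2 expects 20 completers per condition, at alpha 0.05 and beta 0.05.

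**The concern.** The mixed ANOVA takes in the waitlisted patients' later exercise period. The t-test is thus the only test that 9.1 names for exercise against concurrent no exercise, which is the contrast 8.1 asks for.

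A change score gives baseline a fixed weight of 1. If patients with slow baseline times move toward the mean by month 3, the true slope is below 1 and the change score carries avoidable noise. With about 20 completers per arm that noise matters. Baseline TMT-B is already scheduled and precedes randomisation, so adjusting for it needs no new data. Standardised t-scores do not do this job: they are there to interpret the result and are not described as adjusting for a patient's own baseline.

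**Working it through.** **The plan's own figure.** Section 9.2 gives 20 subjects. Section 9.1 says only that the size was "calculated for a large effect change in the main outcome variable", with no number, so 20 cannot be strictly reproduced. Assume d = 0.8 SD of change and a two-sided test (sidedness is not stated).

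- Within-group: n = ((1.960 + 1.645)/0.8)² = 20.3, so 21 by the normal formula and 23 by the t distribution. This is close to 20.
- Two-group comparison of change at 95% power: 41 per arm.
- Power of the planned t-test: 69.3% at 20 v 20 and 81.9% at 20 v 40 (noncentral t; noncentrality 0.8/√(1/20 + 1/20) = 2.53 and 0.8/√(1/20 + 1/40) = 2.92).

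**Equal SDs, common slope.** Var(change) = 2SD²(1 − r) and Var(ANCOVA) = SD²(1 − r²). The ratio is (1 + r)/2, multiplied by 1 + 1/(N − 4) for estimating the slope: 1.0278 at N = 40 and 1.0179 at N = 60. The range of r is assumed.

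| r | Variance ratio, 20 v 20 | Power | Variance ratio, 20 v 40 | Power |
|---|---|---|---|---|
| t-test | 1 | 69.3% | 1 | 81.9% |
| 0.5 | 0.771 | 80.1% | 0.763 | 90.8% |
| 0.7 | 0.874 | 75.0% | 0.865 | 87.0% |
| 0.8 | 0.925 | 72.6% | 0.916 | 85.1% |
| 0.9 | 0.976 | 70.3% | 0.967 | 83.2% |
| 0.95 | 1.002 | 69.2% | 0.992 | 82.2% |

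Break-even is r = (N − 5)/(N − 3): 35/37 = 0.946 and 55/57 = 0.965. As r approaches 1 the loss is 1/36 = 2.8% of variance at 20 v 20 (power 68.1%) and 1/56 = 1.8% at 20 v 40 (81.2%). Simulation at 20 v 20 agreed, with ANCOVA type I error of 0.051.

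**Unequal SDs.** With k = month-3 SD / baseline SD, the ratio is k²(1 − r²)/(1 + k² − 2rk), times 1.0278 at 20 v 20.

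- k = 0.8: between 0.587 and 0.658 for r of 0.5 to 0.9. At r = 0.95 it is 0.0624/0.12 × 1.0278 = 0.53.
- k = 1.2: between 0.895 and 1.025 for r of 0.5 to 0.9. At r = 0.95 it is 0.1404/0.16 × 1.0278 = 0.90.

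The governing quantity is therefore the slope rk, not r alone. Table 1 of section 1.2.1 illustrates this. Time to peak VO2 (SDs 113 and 142, change SD 45) gives r = 0.96, slope 1.21 and a large-sample ratio of 0.72. Peak work rate gives r = 0.89, slope 1.02 and a ratio of 1.00. These are fitness measures in 10 exercised patients, not TMT-B.

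**Slopes that differ by arm, 20 v 40.** Section 1.2.1 expects little improvement in patients who were cognitively normal at baseline, so slopes could differ. Assume baseline SD 1, residual SD 0.6, control slope 1.1 and exercise slope 0.7. The common slope is about (20 × 1.1 + 40 × 0.7)/60 = 0.833.

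- Change: (0.1² + 0.36)/20 + (0.3² + 0.36)/40 = 0.0298.
- ANCOVA: (0.267² + 0.36)/20 + (0.133² + 0.36)/40 = 0.0310.
- Ratio: 1.04 × 1.018 = 1.06 (simulated 1.06-1.07).

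With slopes 0.9 and 0.5 the simulated ratio is 0.93-0.94.

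**Type I error in the unequal-slope cases, 20 v 40.** The t-test stays at or below 0.047. Common-slope ANCOVA has 0.053-0.057 with the ordinary standard error, 0.053-0.056 with HC2 and 0.046-0.049 with HC3. A centred baseline-by-arm interaction has 0.062-0.070 with HC2 and 0.051-0.057 with HC3.

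**The case against.** The strongest reply is that nothing is wrong: randomisation makes the t-test on change valid, and this is a preference between two legitimate analyses. That stands. A reader might infer that the missing covariate biases the comparison or makes its conclusion unreliable. The documents do not support this, because baseline precedes randomisation and both estimators target the same contrast.

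The t-test is also not the analysis labelled primary. That stands too, and limits the weight of the point. A reader might extend the criticism to the mixed ANOVA. On the same two visits its group-by-time test would equal this t-test, but 9.1 gives it other data and another question.

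The gain may be small: at r of 0.8 to 0.9 and 20 v 20 it is one to three power points, and the 11-point figure needs r = 0.5. The 20 v 20 case is also thinly sourced. Section 9.1 speaks of a single exercise group, the combined-and-separate wording in 8.2 governs secondary outcomes, and the expectation in section 2 can be read as within-arm change. For TMT-B the pooled 20 v 40 comparison is the more natural reading, and there unequal slopes can turn the gain into a loss of similar size.

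A reader might also conclude that a correlation of 0.95 or more always removes the benefit. That holds only when the baseline and month-3 SDs are similar.

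**Conclusion.** The point holds as an efficiency improvement that should be made, not as a validity error. Given d = 0.8 SD of change, equal SDs, a common slope and r of 0.5 to 0.9, all of them assumptions, power rises from 69% to 80%-70% at 20 v 20 and from 82% to 91%-83% at 20 v 40. There is no gain when the slope is near 1, which with equal SDs means r of about 0.95 or more. With a common slope the possible loss is much smaller than the possible gain. With strongly unequal slopes at 20 v 40 that asymmetry is not assured.

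Two things remain untouched. Even the most favourable row of the table is below the 95% power in 9.2. And 9.1 restricts the data: "All subjects completing the protocol and not withdrawing or presenting off study criteria will be included in the analyses". Together with replacement of withdrawals (sections 3.1 and 7.3) and the minimum of 30 out of 36 sessions for exercise patients (section 4.4.7), that is a separate bias question which baseline adjustment does not answer.

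**What to change.** In section 9.1, for the baseline-to-month-3 comparison only, replace the independent t-test with an ANCOVA of month-3 TMT-B on randomised arm, with baseline TMT-B as covariate and a common slope. State one scale in advance, seconds or t-scores, for both visits. Report the adjusted arm difference with a 95% confidence interval.

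Use the same model for pooled exercise against control, with one robust standard error named in advance in case slopes differ: HC3, or HC2 if a type I error of about 0.055 is acceptable. Do not use a centred baseline-by-arm interaction. Leave the mixed ANOVA unchanged, and deal with completer-only analysis and replacement separately. Fix the wording before outcome data are seen, so that the choice between change score and ANCOVA is not made afterwards.

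The cost is a wording change and one degree of freedom, with no new data. The statistical downside is at most 2.8% of variance (about one power point) at 20 v 20 with a common slope, and about 6%-7% more variance at 20 v 40 in the unfavourable unequal-slope case above. HC3 also costs some power: at 20 v 20 it gave 77.7% against 80.1% at r = 0.5, and 69.9% against 72.8% at r = 0.8 (simulated), whereas HC2 cost almost nothing. The power cost of HC3 at 20 v 40 was not calculated.
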